The diagnosis of AF, as well as that of other complications, is often made when the patient is symptomatic, requiring immediate and perhaps more aggressive intervention than if an earlier diagnosis had been made. Treatment is generally decided based on the size of the leak, the degree of local contamination, and the associated severity status of the patient. Thus, early diagnosis of AF by clinical, radiological and/or endoscopy is essential to provide immediate treatment through antibiotic therapy, placement of a feeding tube, application of endoscopic therapies, percutaneous drainage of collections, etc., possibly reducing the rate surgical review. For all these reasons, early prediction, diagnosis and treatment of possible major complications (Clavien-Dindo greater than 3), especially AF, are essential to improve the results and prognosis of the disease (6).

Different studies have investigated the usefulness of the use of markers, both pre and postoperative, to predict possible postoperative complications. Recent studies have evaluated different markers in early postoperative stages as predictors of AF and other major complications. These include C-reactive protein (CRP) (7), white blood cell count (RGB) (8), serum albumin (9), tumor necrosis factor  $\alpha$  (TNF  $\alpha$ ), interleukins 1 and 6, the CRP- albumin (CAR) (10-13), modified Glasgow Prognostic Score (mGPS), platelet/lymphocyte ratio and neutrophil/lymphocyte ratio (4) among others.

After carrying out a thorough bibliographic search, the small number of quality prospective studies in this area has been observed, most of them being retrospective or systematic reviews of retrospective studies.

CRP is one of the most studied inflammatory markers related to AF. It is mainly synthesized in the liver in response to proinflammatory cytokines, as an acute phase response protein, and its levels correlate with the severity of inflammation (14). CRP levels increase after surgery and commonly peak after 48 hours (15,16), subsequently decreasing in patients with an uncomplicated postoperative course. Therefore, CRP is especially valuable as a negative test, and a normal or falling CRP level on the third and fifth postoperative days (POD) can help predict which patients are not likely to develop AF (17). Although several prospective

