## OBJECTIVES

Based on the hypothesis of the study, the main and secondary objectives of this study are established:

- Main goal:

\*Design a predictive model based on clinical and analytical variables that allow identifying patients with a high risk of anastomotic leak (main variable) during the postoperative period of esophagogastric surgery.

- Secondary objectives:

\* Design a predictive model based on clinical and analytical variables that allow identifying patients at high risk of other major complications (Clavien-Dindo greater than 3) during the postoperative period of esophagogastric surgery.

\* Individually describe the postoperative evolution of the clinical and analytical parameters studied in patients without major complications or AF and those who did suffer from any of them.

\* Describe the complications and types of AF diagnosed in the study.

\* Assess the day AF was diagnosed and the treatment used for its possible resolution.

\* Assess the day AF was diagnosed and hospital stay.

\* Compare the preoperative Glasgow prognostic score (mGPS) and the biochemical value of inflammatory markers (CRP, Interleukin 6 (IL-6) and procalcitonin) and the appearance of AF.

\* Assess the AF resolution capacity of each technique used.

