### 4.- Sample size

The purpose of the study is to recruit as many patients as possible from all national centers who wish to participate.

For an alpha error of 5% (95% confidence) with a precision of 3% and estimating a number of patients with major complications (including AF) around 30%, the calculation of the sample size yields a total of 847 patients. However, the final sample size may be smaller depending on the proportion of complications detected and the statistical and artificial intelligence models to create the predictive model will be adapted to the event rate provided by the recruited sample.

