### 2.- Data análisis

The statistical study will be carried out with the help of the SPSS® version 23.0 software for Windows, using the MATLAB® programming environment for the preparation of the predictive model based on artificial neural networks (ANN).

In the first place, a descriptive analysis will be carried out, both of the sociodemographic and clinical variables, as well as of the analytics and the results of the study.

To describe the quantitative variables that follow a normal distribution, the mean and standard deviation will be used, and the median and interquartile range for those that do not follow a normal distribution, as well as histograms with normality curves for their graphical description.

For the qualitative variables, frequencies and percentages will be used, using bar graphs and/or sectors for the graphic description of those with greater relevance.

A univariate study will be performed to relate the variables studied with the appearance of AF and major postoperative complications. For this, different tests will be used depending on the variable to be studied:

- a) Normal categorical variables: Chi-square test or Fisher's exact test.
- b) Normal continuous variables: Student's t-test.
- c) Non-normal continuous variables: Mann-Whitney U test.

In the results obtained from the univariate study, those variables that show a  $p < 0.1$  after the application of the corresponding tests will be considered as related or candidates to predict AF or major

complications. This value will be considered more conservative, different from the conventionally accepted value of 0.05, with the intention of not ruling out potential variables that could have some influence on the results of the study.

Once the univariate study has been completed, a multivariate study will be carried out, using the logistic regression (RL) method. To do this, a recoding of the variables will be carried out, transforming the categorical variables into dummy variables. It will be verified that the variance inflation factor (VIF) is less than 2 in all cases, thus ruling out important problems of collinearity between the variables.

On the other hand, a predictive model based on artificial neural networks (ANN) will also be developed, using a Multilayer Perceptron, a multilayer neural network of forward connections, without recurrent connections and supervised learning.

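### The marker description pools leaks with other major complications, so it cannot show whether a marker tracks leak or illness in general

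*Combined protocol and SAP*

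**What the plan says.** The relevant item is in the protocol's OBJECTIVES, under the secondary objectives. It plans to "Individually describe the postoperative evolution of the clinical and analytical parameters studied" and names the groups as patients "in patients without major complications or AF and those who did suffer from any of them". That makes two groups: neither event, or at least one of them.

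Other parts of the plan treat leak separately:

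- The main goal is a model for anastomotic leak, which is named as the main variable.
- Another secondary objective is to "Compare the preoperative Glasgow prognostic score (mGPS) and the biochemical value of inflammatory markers" against the appearance of leak.
- DATA COLLECTION AND ANALYSIS, 2.- Data análisis, has univariate tests to "relate the variables studied with the appearance of AF and major postoperative complications", followed by logistic regression and a neural network.

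None of these sections defines a group with a major complication but no leak, or compares such patients with leaks. Section 4.- Sample size gives one pooled rate, "estimating a number of patients with major complications (including AF) around 30" per cent, and no rate for leak alone.

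**The concern.** The study exists to recognise leak early. A patient with another major complication also has deranged markers, and the INTRODUCTION itself says that CRP follows the severity of inflammation. In the two-group description such patients sit alongside the leaks, and both are set against patients with neither event. A gap between the two groups then has several possible explanations: the marker responds to leak, to the other complications, or to both.

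What is at stake is how one secondary objective is read. A reader may take a wide gap as evidence that a marker helps to find leaks, or a narrow gap as evidence that it does not. Either conclusion could be wrong.

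**Working it through.** **Inputs**

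- Pooled event rate 0.30, from 4.- Sample size. The remaining 0.70 have neither event.
- Leak rate in this cohort: not given. I assume 0.10 to 0.16. The upper value is the leak incidence in the retrospective cohort of 330 patients cited in the INTRODUCTION. The lower value has no source in the documents. The INTRODUCTION quotes 0 to 34% across esophagectomy series.
- All leaks are counted in the 0.30 (assumption).
- For illustration only, a marker that is normal with equal variance and shifted by 1 SD in the patients it responds to (assumption).

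The plan has no figure of its own for this contrast. Its one computed figure is 847 patients. The stated inputs give 1.96² × 0.30 × 0.70 / 0.03² = 896.4, so 897, and 847 is not reproduced. I use 847 only to turn percentages into counts, and the point does not depend on it.

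**Step 1: who is in the pooled group**

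- Leak share: 0.10/0.30 = 33%; 0.16/0.30 = 53%.
- Share without leak: 67% and 47%.
- At 847 patients: about 254 pooled, of whom 85 to 136 have a leak and 169 to 119 do not, with about 593 in the comparison group.
- With a leak rate of 5% to 20%, the leak share runs from 0.05/0.30 = 17% to 0.20/0.30 = 67%.

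These ratios give the make-up of the group only. They say nothing about how far a marker would separate the groups.

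**Step 2: what pooling does to a marker**

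For a 1 SD shift, AUC = Φ(1/√2) = 0.76. Where a group is mixed, the AUC is the weighted average over its parts.

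| Marker raised by 1 SD in | Pooled v neither (as planned) | Leak v all non-leak | Leak v major complication without leak |
|---|---|---|---|
| every complicated patient alike | 0.76 | 0.70 to 0.72 | 0.50 |
| leaks only | 0.59 to 0.64 | 0.76 | 0.76 |
| major complications without leak only | 0.67 to 0.62 | 0.44 to 0.46 | 0.24 |

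The mixed entries, at leak rates of 10% and 16%:

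- Row 1: (0.70 × 0.76 + 0.20 × 0.50)/0.90 = 0.70; (0.70 × 0.76 + 0.14 × 0.50)/0.84 = 0.72.
- Row 2: 0.33 × 0.76 + 0.67 × 0.50 = 0.59; 0.53 × 0.76 + 0.47 × 0.50 = 0.64.
- Row 3, pooled: 0.67 × 0.76 + 0.33 × 0.50 = 0.67; 0.47 × 0.76 + 0.53 × 0.50 = 0.62.
- Row 3, leak v all non-leak: (0.70 × 0.50 + 0.20 × 0.24)/0.90 = 0.44; (0.70 × 0.50 + 0.14 × 0.24)/0.84 = 0.46.

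**Step 3: reading the table**

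Pooling raises the apparent separation of the general-illness marker modestly (0.76 against 0.70 to 0.72). It lowers that of the leak-only marker (0.59 to 0.64 against 0.76). In the planned display, a leak-only marker and one that ignores leaks altogether have overlapping values (0.59 to 0.64 and 0.62 to 0.67). The last column separates all three, and the plan does not contain that contrast.

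**The case against.** The objective is secondary and only describes. It sets no test, no selection of markers and no conclusion about leak. Questions about leak itself have their own analyses. The protocol also repeatedly states its aim as leak and/or major complications, and for that aim a comparison of any major trouble with none is legitimate. The wording does not forbid splitting the complicated group. All of this stands, and it keeps the point small. It does not supply the missing contrast: the tests of leak against all other patients also leave specificity open, because most non-leak patients are uncomplicated (a general-illness marker still reaches 0.70 to 0.72 there).

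A reader might also infer that values should stop at diagnosis, because a reoperation for leak changes later marker values. The documents do not support a general cut-off:

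- The Clavien-Dindo grade in 8.2.3 carries no date, and bleeding has no field among the listed complications.
- Ending at diagnosis would leave later leak values to come only from leaks diagnosed later.
- In the cited cohort of 330 patients the mean time to leak diagnosis was 7 days, after the last marker day (day 6). Earlier leaks exist, but their number here is unknown.

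**Conclusion.** The point holds as a limited one. As planned, this description cannot show whether a marker follows leak or illness in general. On the assumed leak rates of 10% to 16%, with all leaks inside the 30%, 47% to 67% of the pooled group would have no leak. The AUC figures illustrate direction only and rest on the assumed 1 SD shift and equal-variance normal markers.

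Two stronger readings are tempting and fail. The first is that the description will overstate every marker's ability to separate leak from no leak; the error can go either way, and for a general-illness marker it is modest. The second is that the pooling distorts the main result; the main model and the univariate tests take leak itself as an outcome and are not touched.

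**What to change.** In the secondary objective, replace the two groups by three: leak; major complication without leak; neither. Patients with a leak and another complication go in the leak group. Describe each marker in all three, and read specificity from leak against major complication without leak.

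Optionally, mark values recorded after the day of leak diagnosis separately rather than ending the series there.

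The cost is one sentence in the objectives and one more group in each table or plot. Leak status and day (8.2) and Clavien-Dindo grade (8.2.3) are already collected. The downside is smaller groups: about 85 to 136 leaks and 169 to 119 other major complications at 847 patients on the assumed rates, and fewer if recruitment ends below that number, which 4.- Sample size allows.

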## INTRODUCTION

Esophageal cancer is the sixth leading cause of cancer death worldwide, with an incidence that has been increasing in recent years. Surgery is the mainstay of curative therapy for fit patients with the ability to tolerate extensive surgical procedures. Postoperative morbidity associated with esophagectomy is high (around 60%) (1), pulmonary complications occur in 20-50% of patients, and anastomotic leak (AF) has a variable incidence depending on the series (0- 34%) (1, 2) with an associated mortality of 5-36% (3). Regarding gastric cancer, it represents the fifth most common and the second most frequent cause of death from cancer worldwide, with a rate of postoperative complications close to 40-50% (4).

Among the postoperative complications, AF is the most feared, presenting a high mortality rate. This complication is not only associated with a longer hospital stay and increased costs, but also with a worse prognosis of the disease and the patient's quality of life (5). The variability in the rate of AF in the literature is due to the lack of a precise definition that is generally accepted by all groups, as well as the need to establish a reliable and unanimous diagnostic method. In addition to possible technical failures, there are many potential risk factors that may be related to the appearance of this complication. Thus, patients with this type of pathology and due to factors such as accelerated metabolism and decreased intake present a high risk of malnutrition, hypoproteinemia and systemic inflammation, which can alter collagen synthesis, reduce tensile strength in the anastomosis, facilitate poor tissue healing and induce anastomotic dehiscence.

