## **7.- Follow up**

The patient will be monitored during the first 90 postoperative days, compiling all the specific variables of this study and the possible complications and mortality that occurred in this period.

During the immediate postoperative period, apart from the care applied routinely in each center, patients should be evaluated daily and the clinical and laboratory variables specified later should be collected on days 1, 2, 3, 4 and 6 postoperatively. In the same way, in this postoperative course, the possible complications that appeared during the hospital stay will be compiled.

Subsequently, if the patient is discharged from the hospital, a follow-up will be carried out in the outpatient consultations at 30 and 90 days to evaluate the possible complications that appear in this period and other variables studied will be completed.

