## **8.2.- PARTS of the DATABASE**

After opening the REDCAP application of the AEC, you can access the data set and the different variables to be collected at each moment of the care process and which will be described in more detail below:

The main outcome variable of the study is ANASTOMOTIC LEAKAGE, a categorical variable divided into the following categories, according to the consensus definitions of the Consensus Group on Complications of Esophagectomy (ECCG) (27), which in this study will be applicable both to fistulas occurred after esophagectomy and after gastrectomy:

- NO: If this complication did not occur.
- I: Defect that does not require specific treatment or that can be treated medically or with diet modification
- II: Defect that requires some intervention, but not surgical, such as: drainage by interventional radiology, prosthesis placement, opening of the wound at the bedside, compression or wound healing.
- III: Defect requiring surgical intervention

In relation to this variable, the following data are also included in the study:

- DAY Dx LEAK (DAY of DIAGNOSIS OF THE ANASTOMOTIC LEAK: ordinal variable that shows the number of the postoperative day on which the diagnosis of the anastomotic leak occurred.
- EDA Dx LEAK (LEAK DIAGNOSIS THROUGH ENDOSCOPY): Dichotomous variable: YES/NO.
- CAT Dx LEAK (DIAGNOSIS OF LEAK BY CAT): Dichotomous variable: YES/NO.

The rest of the variables collected in this study are:

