### **8.2.3.- RESULTS**

- ORAL TOLERANCE BEGINNING DAY: postoperative day number on which the patient begins to tolerate food and/or water orally. Continuous variable expressed in days.
- DISCHARGE DATE (DATE OF INTERVENTION): in day/month/year format

- CLAVIEN DINDO COMPLICATION (CLASSIFICATION OF POSTOPERATIVE COMPLICATIONS ACCORDING TO CLAVIEN-DINDO): Categorical variable divided into the following categories:

- NO COMPLICATION: If this complication did not occur.
- I: Any deviation from the normal postoperative course WITHOUT the need for pharmacological treatment or surgical, endoscopic and radiological interventions Acceptable therapeutic regimens are drugs such as antiemetics, antipyretics, analgesics, diuretics and electrolytes and physiotherapy. This grade also includes open wound infections at the patient's bedside.
- II: Requires pharmacological treatment with medications other than those authorized for grade I complications. Blood transfusions and total parenteral nutrition are also included.
- IIIa: Requires surgical, endoscopic or radiological intervention with local anesthesia.
- IIIb: Requires surgical, endoscopic or radiological intervention under general anesthesia.
- IVa: Life-threatening complication (including central nervous system complications: cerebral haemorrhage, cerebral infarction, subarachnoid haemorrhage, but excluding transient ischemic attacks) requiring Intermediate/Intensive Care Unit management. Single organ dysfunction (includes dialysis)
- IVb: Life-threatening complication (including central nervous system complications: cerebral haemorrhage, cerebral infarction, subarachnoid haemorrhage, but excluding transient ischemic attacks) requiring Intermediate/Intensive Care Unit management. Multi-organ dysfunction.
- V: Death of the patient.

- NECROSIS of the PLASTY: Categorical variable divided into the following categories according to the consensus definitions of the Consensus Group on Complications of Esophagectomy (ECCG) (27):

- NO: If this complication did not occur.
- I: Focal necrosis of the graft identified endoscopically, which does NOT require surgical treatment.
- II: Focal necrosis of the graft identified endoscopically, requiring surgical treatment, but not esophageal diversion
- III: Extensive necrosis of the graft, which requires surgical treatment with resection of the graft and esophageal diversion.

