- DIA Dx NECROSIS (DAY OF DIAGNOSIS OF PLASTY NECROSIS): ordinal variable that shows the number of the postoperative day on which the diagnosis of plasty necrosis occurred

- EDA Dx NECROSIS (DIAGNOSIS OF PLASTY NECROSIS BY ENDOSCOPY): Dichotomous variable: YES/NO.

- CAT Dx LEAK (DIAGNOSIS OF PLASTY NECROSIS BY CAT): Dichotomous variable: YES/NO.

- CHYLOTHORAX: Categorical variable divided into the following categories according to the consensus definitions of the Consensus Group on Complications of Esophagectomy (ECCG) (27):

- NO: If this complication did not occur.
- Ia: Debit less than 1 liter per day - Treatment: changes in the enteral diet
- Ib: Debt greater than 1 liter per day - Treatment: changes in the enteral diet
- IIa: Debt less than 1 liter per day – Treatment: total parenteral nutrition
- IIb: Debt greater than 1 liter per day – Treatment: total parenteral nutrition
- IIIa: Debit less than 1 liter per day - Treatment: interventional radiology or surgery
- IIIb: Debt greater than 1 liter per day - Treatment: interventional radiology or surgery

- DAY Dx CHYLOTHORAX (DAY of DIAGNOSIS OF CHYLOTHORAX): ordinal variable that shows the number of postoperative day on which the diagnosis of chylothorax occurred.

- RECURRENT INJURY: Categorical variable divided into the following categories according to the consensus definitions of the Esophagectomy Complications Consensus Group (ECCG) (27):

- NO: If this complication did not occur.
- Ia: Transient unilateral lesion that does NOT require treatment (dietary modifications allowed)

- Ib: Transient bilateral lesion that does NOT require treatment (dietary modifications allowed)
- IIa: Unilateral injury that requires scheduled and deferred surgical treatment (such as thyroplasty or medialization procedure)
- IIb: Bilateral lesion that requires scheduled and deferred surgical treatment (such as thyroplasty or medialization procedure)
- IIIa: Unilateral lesion requiring urgent or preferential surgical treatment due to episodes of aspiration or respiratory problems (such as thyroplasty or medialization procedure)
- IIIb: Bilateral lesion requiring urgent or preferential surgical treatment due to episodes of aspiration or respiratory problems (such as thyroplasty or medialization procedure)
  
- DAY Dx RECURRENT INJURY (DAY of DIAGNOSIS OF THE RECURRENT NERVE INJURY): ordinal variable that shows the postoperative day number on which the diagnosis of the recurrent nerve injury occurred.
  

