- AF (ATRIAL FIBRILLATION): Dichotomous variable: YES/NO.
  
- DAY Dx AF (DAY of DIAGNOSIS OF ATRIAL FIBRILLATION): ordinal variable that shows the postoperative day number on which the diagnosis of atrial fibrillation occurred.
  
- RESPIRATORY INFECTION: Dichotomous variable: YES/NO.
  
- DAY Dx INFEC RESP (DAY of DIAGNOSIS OF RESPIRATORY INFECTION): ordinal variable that shows the number of the postoperative day on which the diagnosis of respiratory infection occurred.
  
- SURGICAL SITE INFECTION (NOT WOUND): Dichotomous variable: YES/NO.
  
- DAY Dx SURGICAL SITE INFECTION (DAY OF DIAGNOSIS OF SURGICAL SITE INFECTION): ordinal variable that shows the number of postoperative day on which the diagnosis of surgical site infection occurred, not including wound infection.
  
- WOUND INFECTION: Dichotomous variable: YES/NO.
  
- DAY Dx WOUND INFECTION (DAY OF SURGICAL WOUND INFECTION DIAGNOSIS): ordinal variable that shows the postoperative day number on which the diagnosis of wound infection occurred.
  
- MORTALITY: Dichotomous variable: YES/NO.
  
- MORTALITY DAY: ordinal variable that shows the postoperative day number on which death occurred.
  
- CAUSE OF MORTALITY: categorical variable with the following categories:
  - Heart problems: including acute myocardial infarction, heart failure, malignant arrhythmias.
  - Respiratory problems: which includes pneumological conditions with respiratory failure that cannot be corrected
  - Neurological problems: including massive stroke, cerebral edema or brain death.
  - hemorrhagic shock
  - Sepsis and septic shock
  - Tumor progression: defined as progressive deterioration of the patient directly related to the oncological process.
  - Other: Free text to write a summary of the cause of the patient's death, if it cannot be included in the previous categories.
  
- READMISSION: Dichotomous variable: YES/NO.
  
- READMISSION DAY: ordinal variable that shows the postoperative day number on which the readmission occurred.

- CAUSE OF READMISSION (WRITE): Free text to write in summary the cause of the patient's readmission.

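### Complications are to be described to day 90, but the database types only seven besides leak and has no 'other complication' item, so other index-stay events in survivors are not systematically recorded by type or day

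*Combined protocol and SAP*

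**What the plan says.** The Objectives section of the combined protocol and SAP lists, among the secondary objectives, to "Describe the complications and types of AF diagnosed in the study". AF in that sentence is anastomotic leak, and nothing restricts the complications to named types. Section 7 (Follow up) sets a 90-day period for "compiling all the specific variables of this study and the possible complications and mortality that occurred in this period". It adds that "the possible complications that appeared during the hospital stay will be compiled", and provides visits at 30 and 90 days to look for later ones.

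Section 8.2 defines leak first and then opens the remaining list with the words "The rest of the variables collected in this study are". Within that list, 8.2.3 gives typed complication fields, each with a day of diagnosis, such as "NECROSIS of the PLASTY: Categorical variable divided into the following categories" and "CHYLOTHORAX: Categorical variable divided into the following categories". It also holds one overall Clavien-Dindo grade, death with its day and cause, and readmission with its day and a free-text cause.

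**The concern.** The text on objectives and follow-up speaks of complications in general, while the database offers a short closed list. A centre that completes every field correctly has nowhere to record what kind of event occurred if it is not on the list. The protocol itself recognises several such events. The grade IV text mentions cerebral haemorrhage, cerebral infarction and dialysis. The causes of death include haemorrhagic shock, stroke and "Heart problems: including acute myocardial infarction, heart failure, malignant arrhythmias". The Introduction states that after esophagectomy "pulmonary complications occur in 20-50% of patients", yet the only pulmonary field is respiratory infection.

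What is at stake is the table of complications by type, which is the natural product of this objective. It would be incomplete for both operations, and for gastrectomy it would have no procedure-specific entry.

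**Working it through.** The plan gives no figure on this point, so the check is a count of fields followed by a trace of each event class through every field that could hold it.

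**Count.** Typed postoperative complications in 8.2.3 besides leak: graft necrosis, chylothorax, recurrent-nerve injury, atrial fibrillation, respiratory infection, non-wound surgical site infection, wound infection. Total 7, each with a day of diagnosis. Items for any other complication, or free text for index-stay complications: 0.

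**Other routes in 8.2.3.**
- Clavien-Dindo: one categorical variable per patient. It gives severity, with no type and no day.
- Cause of death: gives type and day, but only for the fatal event.
- Cause of readmission: gives type and day in survivors, but only for events that lead to readmission.

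**Trace for a survivor of an index-stay event that does not cause readmission.**

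| Event | Field naming it | What remains |
|---|---|---|
| Haemorrhage | none except as cause of death | undated grade |
| Cardiac other than atrial fibrillation | none except as cause of death | undated grade |
| Stroke | none except as cause of death | undated grade |
| Thromboembolism | none | undated grade |
| Non-infective pulmonary | none except as cause of death | undated grade |
| Pancreatic fistula, duodenal-stump leak | none | undated grade; an infected collection might be entered as non-wound surgical site infection |

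**By operation.** Section 8.2.1 enrols subtotal, total, superior polar and extended total gastrectomy. Section 8.2 applies the leak grading to both operations. Four of the seven fields are not specific to a procedure (atrial fibrillation, respiratory infection and the two surgical infections). The other three (necrosis, chylothorax, recurrent-nerve injury) use definitions from an esophagectomy consensus group. Fields for a complication specific to gastrectomy: 0.

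**Scale.** The documents give no incidence for the unlisted types. Taking the target of 847 in section 4 (Sample size) purely as a denominator, 1% × 847 = 8.47, or about 8 patients per 1% of true incidence. Those who die of the event or are readmitted for it are recorded by type; the rest are not. Section 4 says the final sample may be smaller, in which case the count falls in proportion.

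**The case against.** The strongest reply is that describing the complications can be read as describing those defined in 8.2.3, and that neither modelled outcome depends on type. The second half stands: leak has its own fields, and the major-complication outcome is defined by grade. The first half is possible but strained, because section 7 names complications alongside the specific variables of the study rather than as part of them. If that narrow reading is intended, the objective should say so.

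Several stronger inferences are tempting, and the documents do not support them:
- *These events are identified only when the patient dies.* Readmission has a free-text cause and a day, and atrial fibrillation is coded. Section 8.2.2 also collects creatinine, urine output, haemoglobin and oxygen saturation to day 6. Those values may leave a trace of an event, although they are not a diagnosis.
- *They would be counted as zero.* The Data analysis section describes collected variables. A type without a field has no row, and the patient should still carry a grade.
- *The gastrectomy profile would be largely empty.* Leak, four of the seven typed fields, the grade, death and readmission all apply. What is missing is specific labels.
- *The data could not be recovered.* Centres keep the source records under a unique code, and the Limitations section lets coordinators return errors for correction. Later chart review at every centre would be laborious but possible.
- *False alarms of the leak model could not be explained.* The main infective alternatives to leak are coded with a day, and no objective calls for attributing false positives.
- *The 20-50% pulmonary range gives the size of the gap.* The documents do not split it into infective and non-infective events, so no share can be derived.

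**Conclusion.** The gap is real and limited. Followed as written, the plan cannot deliver complications by type beyond leak and the seven listed. Index-stay events of any other type in survivors leave a single undated Clavien-Dindo grade, unless they cause readmission. The loss falls on one descriptive secondary objective; the leak outcome and the grade-defined outcome are still recorded.

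The size is up to about 8 patients per 1% of true incidence at the 847 target, with no total available from the documents. The conclusion assumes that the list in 8.2 is complete, as its opening words indicate, and that the REDCap form matches it.

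**What to change.** In 8.2.3 add at least one 'other complication' item, repeatable, with type and day of diagnosis, in the format of the existing fields. Free-text entries already exist for cause of death and cause of readmission, so this is not a new kind of field. State in the Data analysis section that complications will be reported by type, separately for esophagectomy and gastrectomy. If the item is not added, restate the secondary objective as describing the listed complications plus the overall Clavien-Dindo grade.

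The cost is a few extra minutes of data entry per patient from information already in the clinical record, with no new test or staff. Free-text types will also need some coding before tabulation. Separate yes/no items for the commoner events would reduce that coding but are not essential.
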